4.1 Investigational Product

An investigational product, also known as investigational medicinal product in some regions, is defined a pharmaceutical form of an active substance or placebo being tested or used as a reference in a clinical study, including products already with a marketing authorization but used or assembled (formulated or packaged) differently than the authorized form, or used for an unauthorized indication, or when used to gain further information about the authorized form.

The investigational product should be stored in a secure area according to local regulations. It is the responsibility of the investigator to ensure that investigational product is only dispensed to study subjects. The investigational product must be dispensed only from official study sites by authorized personnel according to local regulations.

In this protocol, investigational product is: Elotuzumab powder for solution for infusion.

4.1.1 *Elotuzumab*

Before administration the drug product should be stored and prepared as per the instructions in [Appendix 5](#). The dose of elotuzumab to be administered to a subject will be calculated by multiplying the subject's weight (kg) by 10 mg/kg in Cycles 1 and 2 (20 mg/kg for Cycle 3 and beyond). The subject's predose weight on Day 1 of each cycle will be used to calculate the dose for each cycle. Each dose should be infused as per instructions in [Appendix 5](#). The infusion start and stop time will be recorded in the CRF. If the infusion is stopped mid-session for any reason, the stop/start time must be recorded together with an explanation.

4.2 Non-Investigational Product

Other medications used in the study as support or escape medication for preventative, diagnostic, or therapeutic reasons, as components of the standard of care for a given diagnosis, are considered non-investigational products.

In this protocol, non-investigational product(s) are: Pomalidomide (Pomalyst[®]) capsules 1 mg, 2 mg, 3 mg, and 4 mg, dexamethasone tablets and concentrate for solution for IV infusion, or products used for Elotuzumab premedication ([Section 4.5.1.4](#)) or thromboprophylaxis ([Section 3.4.1](#)).

4.2.1 *Pomalidomide*

Pomalidomide is an analogue of thalidomide. Thalidomide is a known human teratogen that causes severe life-threatening human birth defects. If pomalidomide is taken during pregnancy, it may cause birth defects or death to an unborn baby. Females must not get pregnant: (1) for at least 4 weeks before starting pomalidomide, (2) while taking pomalidomide, (3) during any interruptions in pomalidomide treatment and (4) for at least 120 days after their last dose of pomalidomide. Furthermore, subjects taking pomalidomide should refrain from donating blood (until at least 90 days) or sperm (until at least 180 days) after last dose of pomalidomide.

Because of this potential toxicity and to avoid fetal exposure to pomalidomide, pomalidomide is only available under a special restricted distribution program. Each risk management program is country or region specific. Under these programs, only prescribers and pharmacists registered

with the program can prescribe and dispense the product. In addition, pomalidomide must only be dispensed to subjects who are registered and meet all the conditions of the local pomalidomide risk management program or meet all the conditions of the Pomalidomide Pregnancy Risk Prevention Plan. Subjects who have the potential of pregnancy must be instructed about contraception and undergo the scheduled pregnancy tests.

All study participants must be registered into the local, mandatory pomalidomide risk management program or follow the Pomalidomide Pregnancy Risk Prevention Plan, and be willing and able to comply with all requirements.

Please see the US package insert/SmPC for additional information for prescribing to female subjects and male subjects about this restricted distribution program.

Subjects should not break, chew or open the capsules. Pomalidomide should be taken without food (at least 2 hours before or 2 hours after a meal). Only enough pomalidomide for one cycle of therapy will be supplied to the patient each cycle in accordance with the local pomalidomide risk management program or the Pomalidomide Pregnancy Risk Prevention Plan.

WOCBP must have negative pregnancy testing and use contraception methods before initiating pomalidomide.

The trade name of pomalidomide may vary in other countries. In such cases, refer to country trade name.

4.2.2 Dexamethasone

Dexamethasone tablets and solution for IV infusion is considered NIMP for this study and will not be provided by the sponsor. It will be obtained by the investigating sites standard prescribing procedures except where it may be supplied by BMS due to country availability and specific regulatory requirements. Marketed product will be utilized for this study and should be stored in accordance with the package insert or summary of product characteristics (SmPC). See [Table 4.5.1.5-1](#) for dexamethasone dose reduction information if infusion reaction is observed.

4.3 Storage and Dispensing

The product storage manager should ensure that the study drug is stored in accordance with the environmental conditions (temperature, light, and humidity) as determined by BMS. If concerns regarding the quality or appearance of the study drug arise, do not dispense the study drug and contact BMS immediately.

The investigator (or assigned designee, ie, study pharmacist) will dispense the proper number of each strength tablet to the subject to satisfy dosing requirements until the subject's next visit. The subject must be instructed to return all unused study medications in the provided packaging at each subsequent visit.

Procedures for proper handling and disposal of anticancer drugs should be considered.

Study drug not supplied by BMS will be stored in accordance with the package insert.

[figure not shown]
[figure not shown]
[REDACTED]

[figure not shown]
[REDACTED]					
[REDACTED]	[REDACTED]	[REDACTED]	[REDACTED]	[REDACTED]	[REDACTED]
[REDACTED]					
[REDACTED]	[REDACTED]	[REDACTED]	[REDACTED]	[REDACTED]	[REDACTED]
[REDACTED]	[REDACTED]	[REDACTED]	[REDACTED]	[REDACTED]	[REDACTED]
[REDACTED]					
[REDACTED]	[REDACTED]	[REDACTED]	[REDACTED]	[REDACTED]	[REDACTED]
[REDACTED]	[REDACTED]	[REDACTED]	[REDACTED]	[REDACTED]	[REDACTED]

[REDACTED]

[REDACTED]					
[REDACTED]	[REDACTED]	[REDACTED]	[REDACTED]	[REDACTED]	[REDACTED]
[REDACTED]	[REDACTED]	[REDACTED]	[REDACTED]	[REDACTED]	[REDACTED]
[REDACTED]	[REDACTED]	[REDACTED]	[REDACTED]	[REDACTED]	[REDACTED]

[REDACTED]

4.5.2 Guidelines for Elotuzumab Infusion in Subjects with Infusion Reactions

4.5.2.1 Grade 1 Infusion Reaction

For Grade 1 elotuzumab infusion-related reactions, by definition, do not require intervention. However, increased monitoring is recommended.

4.5.2.2 Grade \geq 2 Infusion Reaction

Infusion reactions during the elotuzumab infusion: For a Grade \geq 2 elotuzumab infusion-related reaction, the infusion must be interrupted. The subject should be treated as clinically indicated with one or more of the following medications or interventions: antiemetics, antihistamines, analgesics, corticosteroids, leukotriene inhibitors, oxygen inhalation, epinephrine, bronchodilators, or other supportive measures as indicated. Subjects with a Grade 4 elotuzumab infusion reaction, see Section 4.5.2.3.

For Grade 2 or 3 infusion reactions, once the elotuzumab infusion-related reaction has resolved to Grade \leq 1, the infusion can be restarted at 0.5 mL/minute. If symptoms do not recur after 30 minutes, the infusion rate may be increased in a stepwise fashion starting at a rate per investigator's discretion, and increasing up to a rate per investigator's discretion, up to a maximum of 5 mL/minute.

Subjects who experience an infusion reaction require vital signs to be monitored every 30 minutes for 2 hours after the end of the elotuzumab infusion. If the elotuzumab infusion reaction recurs, the infusion must be stopped and not restarted on that day. Appropriate therapy should be administered to address the subject's signs and symptoms. The infusion can be reattempted at the next protocol defined infusion time point at the investigator's discretion with additional premedication as described in [Table 4.5.1.5-1](#).

Infusion reactions after the completion of elotuzumab infusion: Should a Grade \geq 2 infusion reaction occur following completion of an elotuzumab infusion, the subject should be treated as above.

Elotuzumab infusions on subsequent weeks after a prior Grade 2 or 3 infusion reaction: Subjects with a prior Grade 2 or 3 infusion reaction during Cycle 1 should have the subsequent infusion started at 0.5 mL/min. The infusion rate may be escalated in a stepwise fashion (0.5 mL/minute every 30 minutes) to a maximum of 5 mL/minute on that day. If no Grade \geq 2 infusion reaction occurs, the next infusion may be increased in a stepwise fashion starting at a rate per investigators' discretion, and up to a maximum of 5 mL/minute. If tolerated, all subsequent infusions may start at a rate per investigator's discretion, up to a maximum rate of 5 mL/minute.

Contact the Medical Monitor with any questions regarding elotuzumab infusion rate escalation.

4.5.2.3 Grade 4 Infusion Reaction

Acute symptoms should be managed as described in Section 4.5.2.2. Elotuzumab must be permanently discontinued. Subjects may continue with pomalidomide and dexamethasone per protocol.

[figure not shown]
4.5.3 Dose Delay, Interruption, or Discontinuation, All Subjects

If the dose of one drug in the regimen (ie, pomalidomide, dexamethasone, or elotuzumab) is delayed, interrupted, or discontinued, the treatment with the other drugs may continue as scheduled. However, if dexamethasone is delayed or discontinued discuss ongoing elotuzumab administration with the medical monitor. Also see [Section 3.5](#) for delays in study drugs.

Each cycle is 28 days. While dose delays or interruptions are permitted, the start of each cycle cannot be delayed and is fixed (ie, anchored) relative to Cycle 1 Day 1. Adjustments to the Cycle 1 Day 1 anchored schedule should not be performed. Should the start of a cycle be delayed, it is expected the following cycle begin as anchored to Cycle 1 Day 1. For example, if a subject is unable to start Cycle (X) until 3 days after the anchored start date, all assessments should be recorded on Cycle (X) Day 3. The following cycle should begin on Day 1 (not Day 3) of Cycle (X+1). Missed doses should be skipped, not delayed, if not given within the allowed window.

Subjects may continue on study therapy even if components of the study therapy must be discontinued. For example, a subject on pomalidomide and dexamethasone may continue on study therapy even if dexamethasone must be discontinued for an adverse event. Likewise, a subject on the elotuzumab arm may continue on study therapy if elotuzumab must be discontinued for an adverse event or other reason. Subjects are considered still on study therapy even if they continue solely on pomalidomide or dexamethasone.

Please consult the BMS Medical Monitor or any questions regarding dose interruption or study

Subjects should be instructed that if a dose of pomalidomide has been missed and it has been less than 12 hours since the subject’s regular dosing time, to take pomalidomide as soon as the subject remembers. If it has been more than 12 hours, the dose must be skipped. Subjects should not take 2 doses at the same time

4.5.4 Recommended Dose Reduction

The criteria presented in this section for dose modification of dexamethasone and pomalidomide are meant as general guidelines. They are based on current US standards of clinical practice. Local standards may differ and may be followed. Dose modification may occur in the setting of lower grade toxicity if the investigator, in consultation with the Medical Monitor/Sponsor, believes that it is in the interest of subject safety.

4.5.4.1 Elotuzumab

No dose reduction is allowed for elotuzumab.

4.5.4.2 Dexamethasone

Dexamethasone dose reductions for toxicity must be performed as clinically indicated. Recommended management is described in Table 4.5.4.2-1 and Table 4.5.4.2-2. Deviations to the recommended dose reductions are allowed based on the clinical judgment of the investigator.

CTCAE Category	Adverse Event	Treatment Adjustment
Gastrointestinal	Dyspepsia, gastric or duodenal ulcer, gastritis Grade 1 - 2 (requiring medical management)	Treat with a proton pump inhibitor. If symptoms persist despite above measures, decrease by 1 dose level.
	≥ Grade 3 (requiring hospitalization or surgery)	Hold dexamethasone until symptoms are adequately controlled. Reduce by 1 dose level and resume along with concurrent therapy with a proton pump inhibitor. If symptoms persist despite above measures, reduce to dose level -3 (dose withheld).
	Acute pancreatitis	Reduce to dose level -3(dose withheld).
Cardiovascular	Edema ≥ Grade 3 (limiting function and unresponsive to therapy or anasarca)	Use diuretics as needed, and decrease dexamethasone by 1 dose level. If edema persists despite above measures, decrease by another dose level.
Neurology	Confusion or Mood alteration ≥ Grade 2 (interfering with function ± interfering with activities of daily living)	Hold dexamethasone until symptoms resolve. Decrease by 1 dose level and resume. If symptoms persist despite above measures, decrease by another dose level.

Table 4.5.4.2-1: Dexamethasone Dose Reductions		
CTCAE Category	Adverse Event	Treatment Adjustment
Musculoskeletal	Muscle weakness \geq Grade 2 (symptomatic and interfering with function \pm interfering with activities of daily living)	Hold dose until muscle weakness is \leq Grade 1. Decrease dexamethasone by 1 dose level and resume. If weakness persists despite above measures, decrease by another dose level.
Metabolic	Hyperglycemia \geq Grade 3 or higher	Treat with insulin or oral hypoglycemics as needed. If uncontrolled despite above measures, decrease by 1 dose level until glucose levels are satisfactory.
Constitutional	Insomnia \geq Grade 2	Decrease by 1 dose level and resume.

Dose reduction for persistent Grade 2 or Grade \geq 3 AEs believed to be related to dexamethasone and not listed above are permitted. Dose reductions should follow the guidance in [Table 4.5.4.2-1](#) and [Table 4.5.4.2-2](#).

For subjects receiving elotuzumab, regardless of dexamethasone dose reduction, at least 8 mg of the weekly dexamethasone dose must be administered IV as part of the premedication for elotuzumab with the remainder of the weekly dexamethasone dose administered orally as described in [Section 4.5.1](#). Contact the Medical Monitor to discuss dexamethasone IV premedication for subjects in the investigational arm who reach dose level -3 and must discontinue dexamethasone due to dose limiting toxicity.

On days without elotuzumab, no IV dexamethasone should be administered.

Table 4.5.4.2-2: Dexamethasone Dose Levels				
Dose Level	Reducing Dexamethasone on Weeks with Elotuzumab		Reducing Dexamethasone on Weeks Without Elotuzumab	
	PO	IV	PO	IV
0	\leq 75 years old - 28 mg	8 mg	\leq 75 years old - 40 mg	N/A
	$>$ 75 years old - 8 mg		$>$ 75 years old - 20 mg	
-1	\leq 75 years old - 12 mg	8 mg	\leq 75 years old - 20 mg	N/A
	$>$ 75 years old - 2 mg		$>$ 75 years old - 12 mg	
-2	\leq 75 years old - 0 mg	8 mg	\leq 75 years old - 12 mg	N/A
	$>$ 75 years old - 0 mg		$>$ 75 years old - 8 mg	
-3	\leq 75 years old - 0 mg	Contact Medical Monitor	\leq 75 years old - 0 mg	N/A
	$>$ 75 years old - 0 mg		$>$ 75 years old - 0 mg	

4.5.4.3 Pomalidomide

Below are the recommended dose adjustments for the management of thrombocytopenia and neutropenia judged by the investigator to be related to pomalidomide. Information in Table 4.5.4.3-1 and Table 4.5.4.3-2 is based on pomalidomide prescribing information, which contains additional guidance on pomalidomide dosing^{43 44}.

Table 4.5.4.3-1: Treating Thrombocytopenia Related to Pomalidomide	
When Platelet Count:	Recommended Course:

 Fall to < 25,000 per mm³ Return to > 50,000 per mm³ 	
 Interrupt pomalidomide treatment, follow Complete Blood Count weekly. Resume pomalidomide at 3 mg daily

 For each subsequent drop < 25,000 mm³ Return to ≥ 50,000 mm³ 	
 Interrupt pomalidomide treatment Resume pomalidomide at 1 mg less than previous dose

Table 4.5.4.3-2: Treating Neutropenia Related to Pomalidomide	
When Neutrophil Count:	Recommended Course:

 Fall to < 500 per mm³ or febrile neutropenia (fever ≥ 38.5°C and ANC < 1,000 mm³) ANC returns to ≥ 1000 per mm³ 	
 Interrupt pomalidomide treatment, follow Complete Blood Count weekly. Resume pomalidomide at 3 mg daily

 For each subsequent drop < 500 mm³ Return to ≥ 1000 mm³ 	
 Interrupt pomalidomide treatment Resume pomalidomide at 1 mg less than previous dose

ANC, absolute neutrophil count. In case of neutropenia, consider the use of growth factors in subject management.

If necessary to co-administer strong inhibitors of CYP1A2 in the presence of strong inhibitors of CYP3A4 and P-glycoprotein, consider reducing pomalidomide dose by 50%.^{43,44}

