Protocol Title: An Open Label, Randomized Phase 2 Trial of Pomalidomide/Dexamethasone With or Without Elotuzumab in relapsed and refractory Multiple Myeloma

Investigational Product(s), Dose and Mode of Administration, Duration of Treatment with Investigational Product(s):

See **Study Schema** for details

Control Arm

Pomalidomide: 4 mg PO QD Days 1-21 of each cycle

Dexamethasone:

- Subjects \leq 75 years old: 40 mg PO Days (1, 8, 15 and 22) of each cycle
- Subjects $>$ 75 years old: 20 mg PO Days (1, 8, 15 and 22) of each cycle

Elotuzumab Arm

Elotuzumab:

- Cycle 1 - 2: 10 mg/kg IV Days 1, 8, 15 and 22 of each cycle
- Cycle 3 and beyond: 20mg/kg IV Day 1 of each cycle

Pomalidomide: 4 mg PO QD Days 1-21 of each cycle

Dexamethasone: Days 1, 8, 15 and 22 of each cycle

- Subjects \leq 75 years old: weeks with elotuzumab dosing: 28 mg PO + 8 mg IV and 40 mg PO on non-elotuzumab dosing weeks
- Subjects $>$ 75 years old: weeks with elotuzumab dosing: 8 mg PO + 8 mg IV and 20 mg PO on non-elotuzumab dosing weeks

A cycle is defined as 28 days. Treatment with study drug continues until disease progression, unacceptable toxicity (adverse event related to study drug), or subject meets other criteria for discontinuation of study drug outlined in [Section 3.5](#).

Study Phase: 2

[figure not shown]
Primary Objective:

- To compare progression free survival (PFS) between treatment arms

Secondary Objectives:

- To compare objective response rate between treatment arms
- To compare overall survival between treatment arms

Study Schema

Study Population:

Subjects who are diagnosed with relapsed and refractory multiple myeloma defined as:

- 1) Must have received ≥ 2 prior lines of therapy (See [Appendix 1](#)) which must have included at least 2 consecutive cycles of lenalidomide and a proteasome inhibitor alone or in combination.
- 2) Documented refractory or relapsed and refractory (R/R) multiple myeloma
- 3) Refractory (progressed on or within 60 days of treatment) to their last treatment.
- 4) Subjects must have failed treatment with a proteasome inhibitor and lenalidomide in one of the following ways.
 - a) “Refractory” to proteasome inhibitor and lenalidomide, and to their last treatment.
 - b) “Relapsed and refractory”= patients had achieved at least a partial response to previous treatment with proteasome inhibitor or lenalidomide, or both, but progressed within 6 months, and were refractory to their last treatment

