7.4.2.6 Pomalidomide Dose Reduction

Reduction of Pomalidomide will be computed based on the actual dose received. In any study day (excluding, cycle 1, day 1), the drug will have a calculated reduction compared to the previous day, if the actual level of the administered dose is below the actual level of the administered dose in the previous instance. The information for this analysis will be derived programmatically, using the total daily dose on the “Record of Study Medication - pomalidomide” eCRF page.

The daily dose levels are defined as follows:

- Dose level 0 or full dose (4mg)
- Dose level -1 (3mg)
- Dose level -2 (2mg)
- Dose level -3 (1mg)

The number and percentage of subjects with a dose reduction, and the lowest dose level achieved per subject (-1, -2, -3), will be presented by treatment group.

The reason for dose reduction as reported by the investigator will be tabulated for all instances with a calculated reduction based on the dose modification for Pomalidomide page. A category “unknown” will be defined for all calculated reductions with no reason reported by the investigator.

A by-subject listing of dose reductions will be generated. This will include all reported reductions per investigator, regardless of whether it met the requirements for a calculated reduction.

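### The fixed 3 mg restart in both pomalidomide cytopenia tables, read literally, raises the dose of a subject already at 2 mg or 1 mg (minor safety wording error)

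*Protocol*

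**What the plan says.** The Synopsis gives the same pomalidomide schedule in both arms: "Pomalidomide: 4 mg PO QD Days 1-21 of each cycle".

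Protocol Section 4.5.4.3 has two tables for cytopenias that the investigator relates to pomalidomide: Table 4.5.4.3-1 for platelets below 25,000 and Table 4.5.4.3-2 for neutrophils. Each has two rows.

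- **Row 1, both tables:** interrupt, wait for recovery, then "Resume pomalidomide at 3 mg daily". No condition is placed on the current dose.
- **Row 2, both tables:** after a further fall, "Resume pomalidomide at 1 mg less than previous dose".

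In the neutropenia table the two triggers differ. Row 1 covers a count below 500 "or febrile neutropenia (fever ≥ 38.5°C and ANC < 1,000 mm³"). Row 2 says only "For each subsequent drop < 500 mm³". A note under that table adds: "In case of neutropenia, consider the use of growth factors in subject management".

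Neither table refers to reductions made under the other. The same section suggests halving pomalidomide when certain strong inhibitors must be given together. Section 4.5.4 describes the criteria as general guidelines, lets local standards apply, and allows dose changes for lower-grade toxicity in consultation with the Medical Monitor or sponsor. SAP Section 7.4.2.6 lists 3, 2 and 1 mg as dose levels below 4 mg.

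**The concern.** Row 1 is an absolute dose and row 2 is a relative step. An absolute restart of 3 mg lowers the dose only if the subject was on 4 mg. The tables run separately by cell line, so a subject can be at 2 mg or 1 mg from earlier falls in one line and then have a first fall in the other. Row 1 of the second table then recommends a restart above the dose at which the new severe cytopenia occurred, in a section headed as dose reduction. No visible text forbids this.

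The neutropenia table has a second, smaller gap. A febrile neutropenia with a count of 500 to 999 is a trigger in row 1 but is not named in row 2, so a site has no clear instruction when one follows an earlier neutropenic event.

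What is at stake is the safety of individual subjects, not the primary comparison.

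**Working it through.** **Inputs.** Starting dose 4 mg (Synopsis). Row 1 restart 3 mg and row 2 restart equal to the previous dose minus 1 mg (Section 4.5.4.3). Halving for strong inhibitors (same section). Dose levels 3, 2 and 1 mg (SAP Section 7.4.2.6).

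**The plan's own figure.** One step down from the starting dose is 4 − 1 = 3 mg, which matches row 1. For a subject on 4 mg the table works as intended.

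**Row 1 at other doses.** Relative change = 3 / (dose at the fall) − 1.

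| Dose at the fall | Restart | Change |
|---|---|---|
| 4 mg | 3 mg | 3/4 − 1 = −25% |
| 3 mg | 3 mg | 3/3 − 1 = 0% |
| 2 mg | 3 mg | 3/2 − 1 = +50% |
| 1 mg | 3 mg | 3/1 − 1 = +200% |

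**How a subject gets there through cytopenias.** Let P be platelets below 25,000 and N a neutrophil count below 500. The first event of each type takes row 1 and later ones of the same type take row 2.

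- Two episodes: PP and NN give 4-3-2; PN and NP give 4-3-3. None of the 4 orders gives an increase.
- Three episodes:

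| Order | As written | With the restart capped at the dose at the fall |
|---|---|---|
| PPP, NNN | 4-3-2-1 | 4-3-2-1 |
| PNP, PNN, NPP, NPN | 4-3-3-2 | 4-3-3-2 |
| PPN, NNP | 4-3-2-**3** | 4-3-2-2 |

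So 2 of the 8 three-episode orders end in an increase.

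- Four episodes: PPPN and NNNP give 4-3-2-1-3, the only 2 of 16 orders with a 1 to 3 mg restart.

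These are counts of possible orders, not frequencies. The documents give no rates for these events.

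**Another route.** Halving for strong inhibitors gives 4 × 0.5 = 2 mg. A first fall in either line then restarts at 3 mg, so one episode is enough. The route is narrow: Section 3.4.3 asks sites to avoid such co-administration unless it is medically necessary.

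**Febrile neutropenia.** Suppose two neutrophil falls below 500 (4-3-2 mg) are followed by a febrile neutropenia with a count of 500 to 999. Row 2 does not name it. If row 1 means the first event only, no row applies. If row 1 applies whenever its trigger is met, the restart is 3 mg, an increase from 2 mg. The text does not settle which, so no order containing such an event is counted above.

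**Comparison within the protocol.** Dexamethasone Table 4.5.4.2-1 uses relative steps such as "Decrease by 1 dose level and resume". Its only absolute step goes to the lowest level, where the dose is withheld. Neither form can raise a dose.

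**The case against.** The strongest case is that nobody would escalate on this text. The tables are recommendations, local standards may be followed, and Section 4.5.3 sends questions about dose interruption to the Medical Monitor. Prescribers are registered under a restricted programme, and each supply covers one cycle. The tables are based on the prescribing information, which Section 4.5.4.3 says holds further dosing guidance; sites are given the package insert (Section 5.2). That source, or the blacked-out text ahead of Section 4.5.2, may already contain a cap. All of this stands and keeps the point small. It does not alter the wording of the table a site would consult, which recommends the higher dose without qualification.

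Three stronger readings are tempting but not supported.

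- **That a repeat febrile neutropenia is definitely sent back to 3 mg.** This requires row 1 to mean the first event for count falls but every event for febrile neutropenia. The table may simply be silent.
- **That restarting at 3 mg from 3 mg is also an error.** Resuming at the same dose after a first neutropenia, with the growth-factor support that the table note and Section 3.4.2 allow, is an arguable clinical choice.
- **That the SAP settles the dosing question.** SAP Section 7.4.2.6 counts a reduction only "if the actual level of the administered dose is below the actual level of the administered dose in the previous instance". By that definition a 2 to 3 mg restart is not a reduction, but this is a rule for tabulating doses, not for giving them.

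**Conclusion.** The point holds as a minor safety wording error. As written, row 1 of both tables recommends a restart 50% above a current dose of 2 mg and 200% above a current dose of 1 mg. By the cytopenia route this takes at least three severe episodes for the first and four for the second; by the inhibitor route one episode is enough for the first. The gap for repeat febrile neutropenia is an omission whose consequence is unclear.

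The conclusion rests on three assumptions: that row 1 means the first fall in that cell line, which is inferred from row 2's reference to subsequent drops; that the two tables operate independently, since neither mentions the other; and that no cap exists in text that could not be seen. How many subjects would be affected is unknown.

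A reader might infer a bias between arms or an effect on the analysis. The documents do not support that: the tables apply to both arms, and no sample-size, power or significance figure depends on them.

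**What to change.** 1. In row 1 of both tables, keep "Resume pomalidomide at 3 mg daily" and add: *but never above the dose at the time of the fall*.
2. In row 2 of Table 4.5.4.3-2, after "For each subsequent drop < 500 mm³", add the row 1 wording "or febrile neutropenia (fever ≥ 38.5°C and ANC < 1,000 mm³"), so that repeat febrile neutropenia has a stated action.
3. At 1 mg, ask for discussion with the Medical Monitor before resuming. Row 2 gives 1 − 1 = 0 mg there, and change 2 would extend that stop to repeat febrile neutropenia.

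Whether a subject at 3 mg should resume at 3 mg or step to 2 mg should be left to the prescribing information; the cap is compatible with either.

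The cost is a short clarification to two tables, with no new data or procedures. The downside is slightly lower pomalidomide exposure in the few subjects affected. For example, a subject held at 2 mg instead of going back to 3 mg takes 2 × 21 = 42 mg per cycle rather than 3 × 21 = 63 mg.
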